Netflix and Move Study protocol 2020/2021

Netflix and Move: Does interrupting streaming in the evening with short bouts of activity impact postprandial glycemia and sleep?

A randomised crossover study.

Funding Agencies: Health Research Council of New Zealand

Principal Investigator: [name]

[contact]

Email: [contact]

Co-investigators: [name]

[name]

[name]

Associate [name]

¹Department of Human Nutrition

²Department of Medicine, Dunedin School of Medicine

³School of Physical Education, Sport, and Exercise Sciences

University of Otago

[name]

Dunedin

New Zealand

1. Project Summary

This study will provide important evidence around how reducing sedentary behaviour in the evening by regularly performing short bouts of resistance activity may improve postprandial metabolism and sleep, both of which are important for cardio-metabolic health. We will conduct a randomised crossover study involving 30 participants. The study will include two experimental intervention sessions each performed in the evening between 5:30 pm and 10:00 pm: 1) uninterrupted sitting; and 2) regular activity breaks, separated by a minimum six-day washout period. Blood samples will be collected intermittently across the intervention session and used to measure glucose, insulin, and triglyceride responses. Sleep duration, efficiency and onset latency will be measured via accelerometry in the 48 h after each intervention session is completed. Mixed model regression will be used to examine differences in the effect of the two interventions in these outcomes.

2. Background

Sedentary behaviour activities performed in a seated or reclining position that involve very low energy expenditure (1) is associated with increased incidence of diabetes, cardiovascular disease, some cancers and overall mortality (2-4). Results from observational studies using accelerometers as an objective measure of sedentary behaviour indicate that the *pattern* in which total sedentary time is accumulated is related to markers of cardio-metabolic health, over and above the total amount of sedentary time (5, 6). Individuals who accumulate sedentary time in long continuous bouts have higher waist circumference, body mass index (BMI), fasting glucose and triglyceride concentrations than those with a similar total sedentary time that is frequently interrupted with light physical activity (5, 6). These associations appear to be consistent across age, sex and ethnic groups (6), and occur even in those who engage in large amounts of leisure time moderate-to-vigorous physical activity (5, 6). Intervention studies have demonstrated that performing regular activity breaks (~ 2 min walking, arm cranking, or 3 min of simple resistance exercises every 20-30 min) reduces glucose and insulin concentrations by up to 39% (7-9) and may also reduce triglyceride concentrations and improve non-esterified fatty acid concentrations (10). Having higher concentrations of postprandial glucose, insulin and triglycerides promote oxidative stress, inflammation and endothelial dysfunction (11-14), all of which contribute to the development of atherosclerosis and cardiovascular disease (14, 15). Non-fasting glucose (16), insulin (17) and triglyceride concentrations (18, 19) also independently predict cardiovascular morbidity and mortality. Regular activity breaks have been shown to reduce postprandial glucose and insulin concentrations in young healthy adults (20), as well as those with obesity (21) and type 2 diabetes (7). These improvements have been shown to persist 24 h after the laboratory based intervention (22), and it is currently unknown when they dissipate. Interestingly, to date, no studies have been performed in a sample which includes participants across the spectrum of BMI categories, even though there has been some suggestion that

the effects of regular activity breaks may differ in individuals with different weight status (23).

For many individuals, the greatest accumulation of sedentary time occurs in an occupational setting. However, recent research indicates that in office workers (24), retired people (25), and those with type two diabetes, (26) the most prolonged, uninterrupted periods of sitting happen *in the evening*. In addition, the average adult also consumes ~45% of their daily energy intake in the evening (27). Elevations in postprandial glucose concentrations associated with both prolonged sitting (20) and higher energy intake may be further exacerbated by the circadian rhythm in insulin sensitivity, with poorer insulin response occurring in the evening compared to the morning (28). To date, a single small study (n=9) has found that performing regular activity breaks in the evening produces reductions in postprandial glycemia and insulinemia (29) that are similar to those observed in the morning (21). However, participants in this study were exclusively obese (29).

Uninterrupted screen time in the evenings may not only result in poorer glycemic control, but also poorer sleep (30, 31). Poor sleep is, in turn, also associated with increased risk of cardio-metabolic disease, poorer mental health and earlier mortality (32). Physical activity, on the other hand has been shown to improve sleep (33). The effects of performing regular activity breaks on sleep has not been investigated.

3. Aim of Study

To investigate the efficacy of performing regular activity breaks during prolonged sitting in the evening as a means of improving postprandial metabolism and overall sleep quality.

4. Objectives

To compare the effects of 4 h of uninterrupted sitting to 4 h of sitting interrupted with 3 min of resistance exercises every 30 min, both during prolonged screen time in the evening, on postprandial glucose, insulin and triglyceride response and sleep duration, efficiency, and onset latency, in a sample of 30 participants across the spectrum of BMI categories.

5. Hypothesis

That performing 3 min of resistance exercise every 30 min to interrupt prolonged sitting during screen time in the evening will improve postprandial metabolism and sleep when compared to uninterrupted sitting.

6. Study Design

This study will be a randomised, crossover trial, in which each participant will complete two 4 h intervention sessions: 1) uninterrupted sitting; and 2) sitting but with a 3 min bout of simple resistance exercise every 30 min. Each intervention session will be separated by 6 days, so they are repeated on the same days of the week.

7. Study Setting/Location

This single site study will be conducted in the Department of Human Nutrition Research Clinic at the University of Otago, Dunedin.

8. Study Population

A total of 30 participants between the ages of 18 to 40 y will be recruited to participate. To provide an even distribution of participants across BMI categories: 10 participants will be normal weight (BMI 20-24.9 kg·m⁻²); 10 participants will be overweight (BMI 25 – 29.5 kg·m⁻²); and 10 will be obese (BMI ≥30 kg·m⁻²)

9. Eligibility Criteria

Participants in this study are required to be predominantly sedentary during the day, therefore we will require participants to:

- Self-report spending, on average, more than 5 h per day (at work or at home), and 2 h in the evening engaged in sedentary behaviour.

Other research indicates that smoking impacts postprandial metabolism, therefore, participants will only be included in the study if they are a non-smoker.

Because we are measuring postprandial metabolism, which can be affected by medications and dietary supplements, participants will only be included if they are not taking any medication or dietary supplements that are known to impact postprandial metabolism, including metformin and niacin.

We will also ask participants not to take part if:

- They have been told by a doctor or other medical professional (such as a physiotherapist) that they should avoid doing physical activity or any of the specific movements used in the simple resistance exercises.
- They have an intolerance or allergy to dairy or gluten as the test meal and snack will contain these foods.

Participants will be asked to gain clearance from their General Practitioner to participate in this study if their responses to the Physical Activity Readiness Questionnaire (PAR-Q) indicate that participating in physical activity may not be medically appropriate.

10. Study Outcomes

Primary Outcome:

The difference in glucose total area under the curve (tAUC) and incremental area under the curve (iAUC) measured over 4 h between the two interventions.

Secondary Outcomes

The difference in insulin total area under the curve (tAUC) and incremental area under the curve (iAUC) measured over 4 h between the two interventions.

The difference in triglyceride total area under the curve (tAUC) and incremental area under the curve (iAUC) measured over 4 h between the two interventions.

The difference in nocturnal mean and tAUC interstitial glucose in each of the two nights following the interventions.

The difference in activity patterns (sleep, physical activity, and sedentary behaviour) in the 48-h following the interventions.

The difference in sleep duration (time spent asleep) in each of the two nights following the intervention.

The difference in sleep efficiency (percentage to time spent asleep between sleep onset and sleep offset) in each of the two nights following the intervention.

The difference in sleep onset latency (the duration from the time sleep was attempted until the onset of sleep is detected) in each of the two nights following the intervention.

11. Study Procedures

Recruitment of participants

Paper and electronic copies of the recruitment flyers advertising the study will be distributed around the university campus, including on Dunedin based/focused social media. Individuals interested in participating will be asked to indicate interest by emailing [contact].

Randomisation

Participants will be block randomised (block size n=6) to complete the two interventions in 1 of 2 possible orders. Randomisation will be stratified by weight status. The randomisation sequence will be generated by [name] using Stata software and concealed electronically. The evening before each participant begins his or her first intervention session, [name] will reveal and assign the next sequential allocation. Participants will not be notified of which intervention session they are completing until they arrive at the clinic on the evening of each intervention session. However, by a process of elimination, they will obviously know what their second intervention will be as soon as they begin their first intervention session.

Study procedures

Consent and screening

The postgraduate research students/research assistant or the PI ([name]) will respond to email enquiries providing the information sheet and a link to the REDCap consent and demographic questionnaire. Once the participants have completed the consent and demographic questionnaire, the responses to the PAR-Q will be checked. If medical clearance is required, the participant will be emailed and asked to contact their GP to gain clearance to participate in the study. Once medical clearance is obtained, or if it is not required, participants will be scheduled to attend an initial introductory session.

At this introductory session, the participant will be asked if they have any further questions about the study. Once any questions have been addressed, they will have their height, weight, and blood pressure (in triplicate 1 min apart; after 15-min seated rest) measured. If blood pressure is greater than 140/90 mmHg and participants have not already obtained medical clearance, then they will be asked to contact their GP to gain clearance to participate in the study. Participants will then be shown a video of the exercises they will be asked to perform in the regular activity breaks intervention and asked to practise these movements with the investigator. Technique will be corrected as necessary. To assess the usual sleep and activity patterns of participants before they start the intervention, participants will be fitted with an ActiGraph or AX3 accelerometer (depending on availability – all participants will be fitted with the same model), at the end of this session, which they will be asked to wear for a seven-day period (24 h a day). Participants will also be asked to complete a sleep and wear time diary over this time.

Standardisation of prior physical activity and diet

The afternoon prior to each intervention session, participants will collect food for their breakfast, morning tea and lunch for the following day. Participants will also be fitted with both an ActiGraph (worn at the wrist to measure sleep and physical activity) and a continuous glucose monitor which they will continue to wear through the intervention session and for the following 48 h. They will also be provided with a sleep and wear-time diary, which they are to complete (by recording times of accelerometer removal and bed and attempted sleep times each day). To minimise the influence of previous activity on outcome measures, participants will be required to avoid all intentional moderate-to-vigorous intensity physical activity and be largely sedentary for 24 h prior to each intervention.

Providing food to participants ensures their food intake is standardised before arriving at the clinic. The breakfast, morning tea and lunch together will provide 55% of each participant's estimated energy requirements (Schofield equation (34), using a physical activity factor of 1.5), with a macronutrient profile of 55% carbohydrate, 15% protein, and 30% fat. Participants will be asked to ensure that all provided food is consumed prior to 2 pm, and to replicate the timing of consumption prior to both intervention sessions. Following 2 pm, participants will refrain from eating until they arrive at the clinic.

Intervention sessions

Uninterrupted sitting intervention: Participants will arrive at the clinic at 5:30 pm. A cannula will be inserted into a forearm vein to allow collection of multiple blood samples. The participant will then rest comfortably for at least 15 min before a baseline sample will be collected. At ~6:00 pm participants will be fed a standardised dinner providing 35% of their estimated energy requirements, with a macronutrient profile of 55% carbohydrate, 15% protein and 30% fat. Participants will be required to consume this meal in 15 min. A snack/dessert will be provided at 8:00 pm, providing the final 10% of the participant's estimated energy intake. Blood samples will be collected hourly for 4 h with additional samples collected 30 and 45 min after each feeding. A total of nine blood samples will be collected (Figure One). During the postprandial period, participants will be required to remain as sedentary as possible, only leaving their chair to use the bathroom when required (timing and duration of bathroom breaks will be recorded by an investigator). Upon completion of the intervention session, participants will return home by car (taxi will be arranged and paid for those who do not have their own transport). Participants will continue to wear the continuous glucose monitor and accelerometers for 48 h. Participants will also be asked to record the times they went to bed, started trying to go to sleep and got up for the day for the two nights directly following each intervention session in the sleep and wear-time diary they will be provided with.

Regular Activity Breaks Intervention: This intervention will follow the same protocol as for the prolonged sitting intervention. However, in addition, participants will perform 3 min of simple resistance exercises every 30 min. Simple resistance exercises will consist of calf raises, half squats, knee raises, and straight leg hip extensions. These exercises will be performed in time with a prepared video with technique cuing commentary. In addition, the investigator will accompany the participant in the activity breaks to provide support and monitor safe technique.

[figure not shown]

Figure 1: Intervention Day timeline

Analytical Methods

Blood samples collected for the analysis of glucose, insulin and triglycerides will be centrifuged within an hour of collection and plasma stored at -80°C until analysis. Insulin analysis will be carried out using the Electrochemiluminescent Immunoassay (1010 Immunoassay System, Roche Diagnostic Elecsys[®], Mannheim, Germany). Blood glucose, and triglycerides will be determined using enzymatic colorimetric methods (Roche diagnostics). All analysis will be carried out in the Department of Human Nutrition Diabetes and Lipid Laboratory at the University of Otago. The individual conducting the analysis will be blinded to intervention.

Accelerometer data processing

Usual activity patterns - From the 7-day wear period prior to completing the intervention sessions, an estimate of habitual time spent sedentary, and in light and moderate-to-vigorous physical activity and asleep will be calculated. These variables will be used to describe the baseline characteristics of the population and investigated as moderators in exploratory analysis, as it is possible that baseline physical activity status impacts the effects of regular activity breaks on glycemic control (35).

Sleep - Accelerometer data, including data from the sleep and wear time diaries will be used to investigate the acute effects of uninterrupted sitting and regular activity breaks on sleep duration (time spent asleep), sleep efficiency (ratio of total time spent asleep compared to the total amount of time spent in bed, between sleep onset and sleep offset) and sleep onset latency (the duration from the onset of self-reported attempted sleep time, to the onset of sleep) for two nights after the intervention.

Qualitative Assessment of Practicality of Performing Regular Activity Breaks in the Evening

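### Blocks of 6 do not fill weight strata of 10, so order balance within strata is left to chance, and the BMI limits leave 29.6 to 29.9 without a stratum (minor)

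*Protocol*

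**What the plan says.** Protocol section 11, Randomisation: "Participants will be block randomised (block size n=6") "to complete the two interventions in 1 of 2 possible orders". It adds: "Randomisation will be stratified by weight status". The allocation ratio within a block is not given, and incomplete blocks are not mentioned.

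Section 8 fixes the strata. The total is 30, made up as "10 participants will be normal weight", "10 participants will be overweight" "and 10 will be obese". The limits printed there end overweight at 29.5 ("10 participants will be overweight (BMI 25 – 29.5") and start obese at 30. Section 9 lists no BMI criterion that would exclude anyone between the two.

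Section 12, Statistical methods, describes a mixed model with condition as exposure, participant as random effect and an adjustment for order of randomisation. It also plans exploratory models run separately by weight status, with effect sizes compared across the groups.

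**The concern.** Six divides the total of 30 but not the stratum size of 10. Blocking within strata is meant to keep the two orders equal in each stratum, and with these numbers it does so only by chance.

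Equal orders matter in a two-period crossover because they cancel any difference between first and second session from the treatment contrast, whatever the model contains. With unequal orders, that protection depends on the analysis model. Section 12 also compares effects between weight groups. If one group leans towards one order and another group towards the other, a period effect could pass for moderation by weight status.

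The BMI gap is a separate matter. A person with a BMI of, say, 29.7 meets section 9 but cannot be placed on a stratified list without an improvised decision.

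**Working it through.** **Inputs.** Block size 6 and two orders (section 11); three strata of 10, total 30 (section 8). Assumed: 3:3 permuted blocks, exactly 10 randomised per stratum, no replacements.

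**Plan's own figure.** 3 × 10 = 30, as stated. The protocol gives no figure for order balance.

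**One stratum.** 10 = 6 + 4. The first block gives 3:3. The first 4 places of the second block follow a hypergeometric distribution:
- P(2:2) = C(3,2) × C(3,2) / C(6,4) = 9/15 = 0.60, so the stratum ends 5:5.
- P(3:1 or 1:3) = 6/15 = 0.40, so the stratum ends 6:4 one way or the other (0.20 each way).

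**Three strata.** P(all 5:5) = 0.60³ = 0.216. P(at least one 6:4) = 1 − 0.216 = 0.784. A simulation of 200,000 runs gave 0.7835.

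**Consequence.** Let π be the mean difference between second and first session. A participant's difference (breaks minus sitting) is the treatment effect plus π in one order and minus π in the other. The plain mean of these differences therefore carries (n₁ − n₂)/n of π. A between-person sequence term does not change this when both sessions are complete; a period term removes it. With period in the model, efficiency relative to equal orders is 4n₁n₂/n².

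| Split | Probability | Share of π carried without a period term | Relative efficiency with a period term |
|---|---|---|---|
| 15:15 | 0.36 | 0 | 1 |
| 16:14 | 0.48 | 2/30 = 0.07 | 0.996 |
| 17:13 | 0.144 | 4/30 = 0.13 | 0.982 |
| 18:12 | 0.016 | 6/30 = 0.20 | 0.96 |
| 6:4 within one stratum | 0.40 | 2/10 = 0.20 | 0.96 |

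The mean absolute share over the whole-trial splits is 0.48 × 2/30 + 0.144 × 4/30 + 0.016 × 6/30 = 0.054. Two strata split 6:4 in opposite directions would differ by 0.20 + 0.20 = 0.40 of π with no true moderation.

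**Other fixed block sizes.** The chance of at least one unequal stratum is 70.4% with blocks of 4 and 81.3% with blocks of 8. It is zero with blocks of 2 or 10, which divide 10.

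**BMI limits.** Read to one decimal, normal weight ends at 24.9 and overweight starts at 25, which leaves no gap. Overweight ends at 29.5 and obese starts at 30, which leaves 29.6 to 29.9 unassigned.

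**The case against.** The strongest reply is that little harm follows. The adjustment for order in section 12 may well mean the order in which a session was done, which in a two-period crossover is period. The coding of that covariate may be settled in an analysis plan that is not shown. On that reading the period effect drops out and only the efficiency loss remains. This stands, and it is why a reader who inferred that the primary estimate is biased would go further than the protocol allows.

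Even with a sequence term only, the imbalance is equally likely in either direction, so its expected effect over randomisations is zero. The protocol gives no size for a period effect, so the result can be stated only as a fraction of it. The 78% also sounds worse than it is: a 6:4 stratum is one person away from 5:5, and 36% + 48% = 84% of trials end 15:15 or 16:14. The by-weight models are exploratory and declared underpowered. All of this stands.

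Incomplete final blocks are common, and the protocol nowhere promises equal orders, so it does not contradict itself on this point. Withdrawals, which section 13 allows at any time, can unbalance any list.

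A reader might also expect that mixing block sizes makes the last places harder to guess. Here it does not. If 10 places must give 5:5, the tenth is always fixed by the first nine. Under the present scheme it is fixed only when the three preceding places in its block are all the same order, with probability 2 × 1/20 = 10%. Past orders are visible to staff, because the investigator does the exercises with the participant (section 11, Intervention sessions). This is a real cost of the fix.

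None of this removes the mismatch between block size and stratum size, or the BMI gap.

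**Conclusion.** The point holds as a minor one. Under the assumptions listed, the stated block size fails to deliver equal orders in at least one weight stratum with probability 78%. No stratum can end worse than 6:4, and the trial no worse than 18:12 (1.6%).

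If period is in the model, the cost is at most 4% of efficiency. If only a between-person sequence term is used, the estimate carries 0.07, 0.13 or 0.20 of any period effect at 16:14, 17:13 or 18:12, and 0.20 within a 6:4 stratum, where it could look like moderation by weight status. The protocol does not settle which model is meant, so neither bias in the main result nor spurious moderation can be asserted.

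The BMI gap is a plain slip in section 8. It needs correcting whatever is done about the blocks.

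**What to change.** Before the first allocation, build the list for each stratum from one block of 4 and one block of 6 in random order. That gives 2 + 3 = 5 participants per order in 10 places. Restate the limits in section 8 so that no BMI falls between overweight and obese.

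If a stratum has already used exactly its first block of 6, make its last 4 places a 2:2 block. If it is past place 6, leave that list unchanged.

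The cost is a new randomisation list and one corrected line in section 8. The downside is more predictable last places, so keep the block sizes and the list hidden from recruiting staff. Section 11 already has the sequence concealed electronically and each allocation revealed the evening before the first session, which limits the risk. Withdrawals may still leave the analysed split unequal.

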Statistical analysis will be performed using Stata version 16. As a crossover design, each person will be compared to themselves and the mean difference between the uninterrupted sitting and regular activity breaks interventions for the whole group is determined. The mean difference in outcome variables between the two interventions will be estimated, along with 95% confidence intervals, using mixed effects regression models, with intervention condition as the exposure variable, participant ID as a random effect, and controlling for randomisation order.

Exploration of effect moderation by weight status and by sedentary and physical activity patterns will be undertaken by running the mixed effects regression models stratified by these moderating variables. While not powered to detect significant differences in these smaller groups, effect sizes will be compared to see if moderation is indicated.

13. Ethical Considerations

The study will be conducted in full conformance with the most current revision of the Declaration of Helsinki, the International Conference for Harmonization of Good Clinical Practice Regulations and Guidelines and the laws and regulations of New Zealand.

Quality assurance

This research will be conducted by researchers who are skilled in the technical aspects of this research study. Students/research assistants working on the research project will be carefully trained and overseen by the named investigators. Standard operating procedures will be developed and adhered to at all times.

Risks/safety considerations

Cannula insertion and blood collection.

There is a risk of discomfort, pain and bruising from the cannula insertion. Participants will be informed of the risks. An experienced nurse or phlebotomist will insert the cannula and ensure strict aseptic technique is followed during blood collection from the cannula to minimise any risk of infection.

While most participants tolerate blood collection from a cannula very well, there are a small percentage of participants who may feel faint during and after collection. All blood samples will be collected with the participant sitting in a recliner, which allows for the participant to be reclined with feet elevated should they feel unwell during cannula insertion or blood collection.

Performing Regular Activity Breaks

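### Nocturnal interstitial glucose is compared on absolute values from a separate monitor fitting in each session, without adjusting for the pre-session night that the same fitting records: a minor loss of precision on one secondary outcome

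*Protocol*

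**What the plan says.** Section 11 (Standardisation of prior physical activity and diet) sets the fitting visit on the day before each session: "The afternoon prior to each intervention session, participants will collect food for their breakfast, morning tea and lunch for the following day". At that visit, "Participants will also be fitted with both an ActiGraph (worn at the wrist to measure sleep and physical activity) and a continuous glucose monitor". The wear period is set in the same sentence: "a continuous glucose monitor which they will continue to wear through the intervention session and for the following 48 h". The Intervention sessions part of Section 11 gives the end of wear: "Participants will continue to wear the continuous glucose monitor and accelerometers for 48 h". Section 1 describes the two sessions as "separated by a minimum six-day washout period".

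Section 10 defines the secondary outcome as "The difference in nocturnal mean and tAUC interstitial glucose in each of the two nights following the interventions". It makes no reference to the night before the session.

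Section 12 (Statistical methods) gives one model for the outcome variables, "with intervention condition as the exposure variable, participant ID as a random effect, and controlling for randomisation order". It contains no pre-session glucose term and no term for the fitting. The protocol states no other use for the pre-session glucose night, and no check of the monitor against the venous samples drawn while it is worn.

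**The concern.** Section 12 relies on each person being compared with themselves. That cancels whatever is stable in a person. It does not cancel an error that is redrawn each time a monitor is fitted. If one fitting reads a little high and the other a little low, the gap between them goes straight into that participant's between-condition difference.

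The same fitting also records a night before the condition is applied, and that night carries information about its offset. The outcome and the model, as written, leave the information unused.

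What is at stake is the width of the confidence interval for nocturnal glucose. Section 2 says it is unknown when the benefit of activity breaks dissipates, and the two post-session nights bear on that. Section 12 gives a detectable difference for insulin, triglycerides and sleep duration but none for this outcome, so a reader has no yardstick for an inconclusive result.

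**Working it through.** **Timeline.** Call the session day 0.
- Fitting is on the afternoon of day -1. The session ends at about 10 pm on day 0 (Section 1), and wear ends 48 h later, at about 10 pm on day 2. Each wear therefore covers one pre-session night and two post-session nights.
- With at least six days between sessions, the second fitting is on day 5 at the earliest, after the first wear has ended. Each condition has its own fitting. That a new sensor unit is used is an inference; a refitted unit would still be a new fitting at a new time.

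**No figure of the plan to reproduce.** The stated 30 participants and 0.4 SD concern the blood AUC outcomes. The SDs below are assumptions.

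**Model.** Let so be the SD of the fitting's offset, taken as constant over the wear, and sw the within-person night-to-night SD.
- Variance of the paired post-session difference: 2(sw² + so²).
- Correlation of the pre-session and post-session paired differences, if both nights have SD sw: r = so²/(so² + sw²).
- Fraction of variance removed by regressing one difference on the other: r².
- Variance of a simple change from the pre-session night: 4sw². This beats no adjustment only if so exceeds sw.

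**Results with sw = 0.3 mmol/L (sw² = 0.09).** The detectable difference is for n = 30, two-sided 5%, 80% power. It equals 0.530 × √variance without the covariate and 0.531 × √variance with it (28 and 27 degrees of freedom).

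| so | r | r² | Detectable, as planned | Detectable, adjusted |
|---|---|---|---|---|
| 0.1 | 0.01/0.10 = 0.10 | 1% | 0.237 | 0.236 |
| 0.2 | 0.04/0.13 = 0.31 | 9% | 0.270 | 0.257 |
| 0.3 | 0.09/0.18 = 0.50 | 25% | 0.318 | 0.276 |
| 0.5 | 0.25/0.34 = 0.74 | 54% | 0.437 | 0.297 |

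With no offset the detectable difference is 0.530 × √0.18 = 0.225. A simple change score gives 0.530 × √0.36 = 0.318 at every offset.

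**Less favourable assumptions.**
- Night SD 0.5 on both nights: offsets of 0.2 and 0.3 give (0.04/0.29)² = 1.9% and (0.09/0.34)² = 7.0%.
- Post-session SD 0.3 but pre-session SD 0.5: r² = so⁴/[(so² + 0.09)(so² + 0.25)], which is 0.0016/0.0377 = 4%, 0.0081/0.0612 = 13% and 0.0625/0.17 = 37% for offsets of 0.2, 0.3 and 0.5.

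**Bias.** In 20,000 simulated trials under no effect (so = 0.4, sw = 0.3, n = 30), type I error was 0.049 and mean bias about zero.

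**Form of the covariate.** These reductions need the within-person slope. If the raw night mean is put into the random-participant model, differences between people pull the slope towards 1, which is close to a change score. In simulation (n = 30, night SD 0.3, offset SD 0.2), the raw form raised the variance of the treatment estimate by about 7% and 25% for between-person SDs of 0.5 and 0.8, and by up to about 60% in other settings tried. Splitting the covariate into within-person deviation and participant mean cost at most about 5% at offset SD 0.1. It cut variance by about 1–7%, 5–24% and 31–53% at offset SDs of 0.2, 0.3 and 0.5.

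**The case against.** The strongest reply is that nothing here is invalid. The paired contrast is unbiased, fitting noise is already in the confidence interval, and covariate choice for one secondary outcome is often left to an SAP, which may exist unseen. Part of this stands: the point is about efficiency, and unused means only that the protocol states no use. It does not remove the point, because the protocol itself defines the outcome on post-session nights and writes out a model without the baseline.

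Two further objections stand as limits.
- **The size is unknown.** The protocol names no device and gives no accuracy figure, so both the offset and its constancy over the wear are assumed. A small offset makes the gain negligible.
- **The pre-session night is an imperfect baseline.** Food is supplied from breakfast on the session day, so the previous evening's dinner is not provided, whereas the first post-session night follows a standardised dinner and snack. Moreover, although "Participants will not be notified of which intervention session they are completing until they arrive at the clinic", Section 11 accepts that the second condition is known by elimination, so behaviour on that pre-session night could be affected by it.

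A reader might infer that the comparison is biased, or that a null nocturnal result would merely be sensor noise. The documents support neither: order is randomised, the check shows no bias, and there is no SD from which to attribute a null result to the monitor.

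**Conclusion.** The point holds as a minor improvement in precision. The text establishes three things: a separate fitting per session, a pre-session night within each wear, and an outcome and model that leave that night out. It follows that any fitting-specific offset adds twice its variance to the variance of the paired difference.

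How much this matters rests on assumed SDs. The plausible gain runs from about nothing (offset SD 0.1) to about half the variance (offset SD 0.5 with night SD 0.3 on both nights).

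The consequence is confined to nocturnal interstitial glucose. This is one of several secondary outcomes; it does not appear in the Section 4 objectives and has no power statement. The primary outcome uses laboratory plasma glucose and is untouched.

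**What to change.** In Section 10 and Section 12, or in the SAP before any data are seen, state that nocturnal mean and nocturnal tAUC are each adjusted for the same summary from the same fitting's pre-session night, over the same clock window. Enter it as two terms: the session's deviation from the participant's two-session mean, and that mean. Equivalently, regress the post-session between-condition difference on the pre-session difference, keeping randomisation order. Do not enter the raw value alone and do not use a simple change score, since both can lose precision when the offset is small. Report the unadjusted contrast alongside.

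No new visit or measurement is needed, since the stated fitting time already captures the night. The costs are one degree of freedom for the within-person slope, a variance increase of up to about 5% if the offset is negligible, and the loss of sessions whose pre-session night is missing, so a rule for those should be written at the same time.
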